1.2 Purpose

MS disease modifying treatments generally target the immune system and may therefore interfere with vaccination responses. The purpose of this study is to understand whether participants can mount an immune response to SARS-CoV-2 modRNA vaccines administered either during continuous siponimod treatment or during a treatment break. Furthermore, the study will investigate the development of anti-SARS-CoV-2 antibody and T-cell titers over six months after participants' vaccination.

2 Objectives and endpoints

Table 2-1 Objectives and related endpoints

Objective(s)	Endpoint(s)
Primary Objective(s)	Endpoint(s) for primary objective(s)

 To estimate the proportion of those achieving seroconversion (i.e. having SARS-CoV-2 serum functional antibodies) after receiving a modRNA vaccine in participants treated concomitantly with siponimod and siponimod treatment break. 	Proportion of participants achieving seroconversion as defined by detection of SARS-CoV-2 serum functional antibodies one week after second dose of vaccine in participants treated concomitantly with siponimod and siponimod treatment break (yes/no)
Secondary Objective(s)	Endpoint(s) for secondary objective(s)

 Describing SARS-CoV-2 serum functional antibody levels in participants treated concomitantly with siponimod versus siponimod treatment break versus first-line DMTs and in patients currently not on a DMT Describing the T-cell response to modRNA vaccines in participants treated concomitantly with siponimod versus siponimod treatment break versus first-line DMTs and in patients currently not on a DMT Describing safety, incl. AEs related to discontinuation and new onset of siponimod treatment and patients developing COVID-19 	
 SARS-CoV-2 serum functional antibody levels one week, one month and six months after second dose of vaccine and additionally one month after an optional booster vaccination in participants treated concomitantly with siponimod versus siponimod treatment break versus first-line DMTs and in patients currently not on a DMT SARS-CoV-2 specific T-cell levels one week, one month and six months after second dose of vaccine and additionally one month after an optional booster vaccination in participants treated concomitantly with siponimod versus siponimod treatment break versus first-line DMTs and in patients currently not on a DMT measured by e.g. enzyme-linked immunosorbent spot (ELIspot) assay from peripheral blood mononuclear cells that were stimulated with SARS-CoV-2 peptide mix AEs, SAEs, incl. patients with clinical confirmed COVID-19, events leading to discontinuation in participants treated concomitantly with siponimod versus siponimod treatment break versus first-line DMTs and in patients currently not on a DMT

2.1 Primary estimands

The primary clinical question in this trial is: What is the proportion of SPMS patients treated with siponimod within the three cohorts defined below which develop an immune response to a SARS-CoV-2 modRNA vaccine?

Of note, this is not a randomized trial, therefore no randomization needs to be preserved and the ITT-principle and the associated estimands framework do not apply. However, this protocol

will keep as close as appropriate to the terminology and the definitions established within that framework.

The justification for the primary estimand is that it will capture whether siponimod treated participants generate functional antibodies to SARS-CoV-2 vaccine as assessed by geometric mean titers.

The following attributes describe the primary estimand:

- **Population:** MS patients divided in three cohorts, each receiving a SARS-CoV-2 vaccination as part of clinical routine: (1) vaccination during continued siponimod treatment; (2) vaccination during a siponimod treatment interruption (of approx. 2-3 months); (3) vaccination in MS patients during continued treatment with first-line DMTs or no DMT. Patients who fail to receive their second dose of vaccine for whatever reason will be included in the analysis as non-responders. Patients who did receive their second dose of vaccine and do not have a valid determination of functional antibodies to SARS-CoV-2 for whatever reason will be excluded from the analysis of vaccine efficacy.
- **Variable:** Receiving the second dose of vaccine and achieving seroconversion as defined by detection of SARS-CoV-2 functional antibodies one week after second dose of vaccine (yes/no)
- **Treatment of interest:** siponimod either continuously applied or with a treatment break for the purpose of the vaccination, or first line DMTs or no treatment as part of clinical routine
- **Intercurrent events:** Failure to receive the second dose of vaccine: These patients will be counted as non-responders.
Missing or invalid determination of functional antibodies to SARS-CoV-2: These patients will be excluded from the efficacy analyses (if they received their 2nd dose of vaccine)
- **Summary measure:** n.a., there will be no formal comparison between cohorts. Response rates will only be calculated within each cohort.

3 Study design

This is a three cohort, multicenter, open-label, prospective study of 60 (optional increase to 90) MS patients currently treated with siponimod or a first-line DMT (as per EU SmPC) or without MS treatment planning to undergo a SARS-CoV-2 modRNA vaccination as part of clinical routine and according to the respective EU SmPC. For each participant, total expected duration of the trial is 56-60 weeks.

- The first cohort will be participants not interrupting their current siponimod therapy for the purpose of a SARS-CoV-2 modRNA vaccination. In case of a booster vaccination, patients in this cohort may also undergo a treatment break which is also covered by the EU SmPC.
- The second cohort will be participants interrupting their current siponimod therapy for the purpose of a SARS-CoV-2 modRNA vaccination (treatment interruption of about 2-3 months).

- The third cohort will be participants receiving modRNA vaccine while on treatment with first-line DMTs (dimethylfumarate, glatirameracetate, interferons, teriflunomide) or no current treatment in clinical routine.

The interventional part of AMA-VACC is limited to the collection of blood samples at specified time-points to analyze levels of SARS-CoV-2 specific antibodies and T-cells as response to the modRNA vaccination in clinical routine.

There are 3 study periods:

1. Screening period:

Participants enter a screening period of up to 1 month to assess eligibility requirements including a blood draw and assessment of SARS-CoV-2 specific antibodies at baseline to exclude any prior exposure to the virus or a vaccination. In case the patient is not eligible for SARS-CoV-2 vaccination by local regulation within this time, the Novartis Medical Advisor should be contacted to discuss further proceeding including re-evaluation of anti-SARS-CoV-2 antibody level and PCR test. Furthermore, a SARS-CoV-2 PCR test will be performed at screening to exclude current COVID-19 infection. In case of a positive test result, the patient has to go into quarantine immediately. Patients are only allowed to continue within the study and receive SARS-CoV-2 vaccination once they received a negative PCR test result.

2. Vaccination period

Patients are vaccinated with a complete cycle of modRNA based SARS-CoV-2 vaccine at the discretion of the treating physician outside the study as part of clinical routine.

- Participants in cohort 1: vaccination will be administered according to EU SmPC under continued siponimod treatment. In case of a booster vaccination, patients in this cohort may also undergo a treatment break which is also covered by the EU SmPC.
- Participants in cohort 2: vaccination will be administered according to EU SmPC after start of the siponimod treatment break.
- Participants in cohort 3: vaccination will be administered according to EU SmPC during continued treatment with first-line MS DMTs or no current treatment.

If suggested by local regulations, patients will be allowed to receive additional SARS-CoV-2 vaccinations (booster or refresher) during the study according to the physician's discretion and as part of the clinical routine. This booster may be any type of SARS-CoV-2 vaccine, depending on local regulations. According to SmPC, siponimod patients in Cohort 1 and Cohort 2 may introduce a treatment break for the purpose of the booster vaccination e.g. in case there was no measurable immune response during the initial vaccination cycle. The decision for such a treatment break is at the discretion of the treating physician and patient.

3. Investigational period

[figure not shown]
Blood samples for SARS-CoV-2 functional antibody titers and T-cells for primary and secondary endpoints will be drawn from all patients 1 week (day 6 - 10), 1 month (day 28 - 35)

and 6 months (week 25 - 27) after completion of vaccination. In case of booster vaccinations an additional blood sample will be collected one month (+/- 1 week after the booster vaccination).

12 months (week 50 – 54) after completion of the vaccination a COVID-19 follow-up call is scheduled to inquire about a possible confirmed COVID-19 disease after the end of the study.

In total, the study duration for each participant is 56-60 weeks, depending on the length of the screening period.

Figure 3-1 Study design

PEP: primary endpoint; d= day, w=week, m=month, vacc= vaccination independent of study site. # vaccination as part of clinical routine. * Number of Vaccinations required and interval depends on SmPC of respective modRNA vaccines. Any kind of SARS-CoV-2 booster/refresher vaccination is allowed in this study, if this is suggested by local regulations and applied as part of clinical routine. ^QIf booster vaccinations are performed as part of clinical routine an additional telephone contact (booster vacc) is scheduled. Furthermore, an additional study visit (booster visit) will be performed one month (+/- 1 week) after the booster vaccination matching all assessments of investigational visit 3. If this booster visit falls within +/- 1 week of the regular visit 3 or later than the telephone contact in month 12, it will not be performed. Timing of visits 1-3: 1 week (day 6 - 10), 1 month (day 28 - 35) and 6 months (week 25 - 27) after completion of vaccination. COVID-19 follow-up call: 50-54 weeks after completion of vaccination

4 Rationale

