9.1.1.1 Replacement policy

Patients failing the screening visit (detectable levels of SARS-CoV-2 serum functional antibodies) will be replaced. Patients successfully screened who do not receive a mod-RNA SARS-CoV-2 vaccination according to EU SmPC within 1 month after screening will be excluded from the study and replaced unless the patient is currently not eligible for SARS-CoV-2 vaccination by local regulation. In this case, the Novartis Medical Advisor should be contacted to discuss further proceeding including re-evaluation of anti-SARS-CoV-2 antibody level and PCR test. Patients developing symptoms of COVID-19 or have a SARS-CoV-2 infection (positive test result) between screening and first vaccination will be excluded from the study and will be replaced.

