## 2.5.4 Supportive analyses

If relevant differences in demographic or other baseline characteristics are observed post-hoc analysis will be performed to adjust the primary endpoint for these inhomogeneities. A logistic regression model would be applied.

The qualitative and (semi)quantitative antibody results towards coronaviridae are analyzed in addition. The first by frequency tables, the latter by sample statistics.

In several patients the booster vaccination was performed before Visit 3 at Months 6, so that the efficacy results were expected to be influenced by this booster vaccination. Therefore, the analyses of seroconversion in SARS-CoV-2 functional antibodies and reactivity to IFNg and IL-2 SARS-CoV-2 were presented for both subgroup of patient who received / did not receive a booster vaccination before Visit 3 at Month 3.

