### **2.8.1 Adverse events (AEs)**

According to the CSP all adverse events starting in the on-treatment period, i. e. the treatment emergent AEs, are analyzed.

The on-treatment period lasts from the date of first administration of study treatment after informed consent to 30 days after the month 12 COVID-19 follow-up call.

The number (and percentage) of subjects with treatment-emergent adverse events will be summarized in the following ways:

- by treatment group (cohort 1-3), primary system organ class and preferred term.
- by treatment group (cohort 1-3), primary system organ class, preferred term and maximum severity

A subject with multiple AEs within a MedDRA primary system organ class is only counted once towards the total of the primary system organ class.

A subject with multiple AEs within a preferred term is only counted once towards the total of the preferred term class.

Separate summaries will be provided for study medication related AEs, death, SAEs, AEs leading to discontinuation and adverse events leading to dose adjustment.

The absolute and relative frequency of COVID-19 infections is presented.

Deaths and serious adverse events are listed in addition.

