## 5.3 Statistical models

### 5.3.1 Primary analysis

The primary parameter “seroconversion” is derived from the laboratory data as follows:

Seroconversion is achieved, when SARS-CoV-2 neutralizing antibodies were not found (“negative”) at the time of screening but SARS-CoV-2 neutralizing antibodies are found (“positive”) at visit 1, visit 2 respectively visit 3.

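### No rule separates infection-induced from vaccine-induced responses after the first vaccination, which matters mainly for the Month 6 antibody and T-cell results

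*Protocol*

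**What the plan says.** **Estimand.** Protocol 2.1 defines the variable as "Receiving the second dose of vaccine and achieving seroconversion as defined by detection of SARS-CoV-2 functional antibodies one week after second dose of vaccine". It lists two intercurrent events. The first is "Failure to receive the second dose of vaccine: These patients will be counted as non-responders". The second is "Missing or invalid determination of functional antibodies to SARS-CoV-2: These patients will be excluded from the efficacy analyses", which applies if the second dose was given. SAP 2.5.1 repeats both.

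**Infection before dose 1.** Protocol 3 and 8.3.1 require an antibody test and a PCR at screening. Protocol 9.1.1.1 adds: "Patients developing symptoms of COVID-19 or have a SARS-CoV-2 infection (positive test result) between screening and first vaccination will be excluded from the study". The population rationale in Protocol 4.1 explains that earlier contact with the virus has to be ruled out if the response to vaccination is to be judged.

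**Infection after dose 1.** No section of either document excludes, censors, reclassifies or separately analyses these patients for efficacy. Protocol 12.1 admits anyone with a valid antibody result at the time point. SAP 5.3.1 defines seroconversion as negative at screening and positive "at visit 1, visit 2 respectively visit 3", whatever the cause. SAP 5.4 removes patients for antibody positivity at screening only. The T-cell endpoints (Protocol Table 2-1, SAP 2.7.1) have no infection condition.

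**Boosters, by contrast.** For boosters given before Visit 3, SAP 2.5.4 states that "the efficacy results were expected to be influenced by this booster vaccination". It therefore shows seroconversion and IFNg/IL-2 reactivity separately for patients with and without one.

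**Where infections are reported.** They appear under safety. SAP 2.8.1 says: "The absolute and relative frequency of COVID-19 infections is presented". SAP 2.8.1.1 lists COVID-19-related adverse events, and Protocol 10.1.1 requires a start date for each event.

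**The concern.** The study asks whether siponimod patients respond to the vaccine. A patient who did not respond, was later infected and then tested positive is scored as a vaccine success. For the seroconversion rate this error can only run upward. In an infected patient who had also responded to the vaccine the rate does not change, but later titres and T-cell counts may be raised, and the six-month course of both is part of the stated purpose (Protocol 1.2).

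The plan's own reasoning points to a rule. It excludes viral contact before dose 1 because that contact would obscure the vaccine response, and it splits the Month 6 results for boosters because they are a second antigen exposure. Infection between dose 1 and Month 6 is the same kind of exposure and is already recorded, yet no efficacy table uses it.

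**Working it through.** **1. The plan's precision.** Protocol 12.6.1 and SAP 3 give half-widths of 20.1, 19 and 17.5 points for n = 20. With 1.96 × √(p(1−p)/20):
- p = 70%: 20.08 points
- p = 75%: 18.98 points
- p = 80%: 17.53 points

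The figures reproduce (normal approximation). The planned Clopper-Pearson intervals have half-widths of 21.2, 20.2 and 19.0 points. This is the scale against which to judge any bias.

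**2. Time at risk from dose 1.** Inputs: dose interval 3 to 4 weeks (Table 8-1), and visit windows of day 6–10, day 28–35 and week 25–27 after the second dose (Protocol 3).
- Visit 1: 21 + 6 = 27 to 28 + 10 = 38 days
- Visit 2: 21 + 28 = 49 to 28 + 35 = 63 days
- Visit 3: 21 + 175 = 196 to 28 + 189 = 217 days

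**3. Expected bias.** The documents give no infection rate, so q (cumulative infection by the visit) is an assumption. Let p be the proportion who would be positive without infection. If infection is independent of response and every infected patient tests positive, the observed rate is p + (1−p)q and the bias is (1−p)q, in points:

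| p | q = 1% | q = 2% | q = 5% | q = 10% |
|---|---|---|---|---|
| 50% | 0.5 | 1.0 | 2.5 | 5.0 |
| 70% | 0.3 | 0.6 | 1.5 | 3.0 |
| 80% | 0.2 | 0.4 | 1.0 | 2.0 |

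The range is 0.2 to 5 points.

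**4. In one cohort of 20.** The bias arrives in whole patients, each worth 1/20 = 5 points. The chance of at least one infected patient, 1 − (1−q)^20, is 18%, 33%, 64% and 88% for q = 1, 2, 5 and 10%. The chance of at least one infection-driven responder at p = 70%, 1 − (1 − 0.3q)^20, is 5.8%, 11.3%, 26.1% and 45.6%.

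With one such patient among 14 positives (Clopper-Pearson intervals):
- as written, 14/20 = 70% (45.7 to 88.1)
- patient left out, 13/19 = 68.4% (43.5 to 87.4)
- patient counted as a non-responder, 13/20 = 65% (40.8 to 84.6)

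**5. Is leaving patients out enough?** Take a stress case: 11 vaccine responders, plus 3 of the 9 non-responders infected and turned positive.
- as written, 14/20 = 70%
- infected left out, 11/17 = 64.7% (38.3 to 85.8)
- infected counted as non-responders, 11/20 = 55% (31.5 to 76.9)

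Leaving them out removes about 5 of the 15 points and leaves about 10, because it also takes non-responders out of the denominator. The case is improbable: three or more infected among nine has a chance of 0.8% at q = 5% and 5.3% at q = 10%. It serves only to show that exclusion alone is not a full correction.

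**The case against.** A reader might infer three stronger things.

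*That the primary result is contaminated.* The derivation rule does apply at Week 1, but exposure is about 27 to 38 days. At an assumed 1% to 2% infection and a response of 50% to 70%, the bias is 0.3 to 1.0 points against an interval of roughly ±20. A patient infected after dose 1 who missed dose 2 would be a non-responder anyway, and the SAP's footnote on analysis sets says every patient received the second dose.

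*That Month 6 rates are inflated by 5 to 15 points, most in the cohort with the weakest response.* This needs one to three infection-driven responders per cohort. The upper end needs a third of non-responders infected. The documents give no infection counts, so neither that rate nor a difference between cohorts is supported. No formal comparison of cohorts is planned.

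*That infection must become an intercurrent event, with infected patients removed from the main tables.* This is a choice between strategies. Exclusion alone can leave most of the bias (step 5). Editing Protocol 2.1 would need an approved amendment (Protocol 14.1), and the SAP's latest revision is already marked as following final data review, so a new exclusion in the primary analysis of an open-label study would be post hoc.

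These objections stand and set the limits of the point. Three others do not remove it. The estimand framework is said not to apply, but the protocol keeps close to its terms and names intercurrent events. The analyses are descriptive, but a rate presented as vaccine response still needs a definition that separates vaccine from infection. The safety listings let a reader find infected patients, but no efficacy result is shown without them.

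**Conclusion.** The gap is real and the correction is worth making as a supportive analysis. From dose 1 onward the plan credits any new positivity to the vaccine. The consequence is likely small at Week 1 and matters chiefly at Month 6, for seroconversion, antibody levels and T-cell reactivity.

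The expected upward bias in a rate is about 0.2 to 5 points. That rests on assumed cumulative infection of 1% to 10%, independence of infection and response, a true response of 50% to 80%, and every infected patient testing positive. If non-responders are infected more often, the bias is larger; the documents do not allow this to be quantified. The effect on titres and T-cell levels cannot be sized from the documents.

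**What to change.** In SAP 2.5.4 and 2.7.1, add a supportive analysis alongside the booster split, labelled as post hoc:

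1. Show seroconversion, antibody levels and IFNg/IL-2 reactivity at Visits 1, 2 and 3, chiefly Month 6, without samples taken after a confirmed SARS-CoV-2 infection.
2. For each cohort, show how many patients are set aside and their last result before infection.
3. Show the seroconversion rate again with infected patients who were negative before infection counted as non-responders. For an infection before Visit 1 the only earlier result is the negative screening test, so this version is a conservative figure there.

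Leave the primary Week 1 estimand and the all-results tables unchanged; no change to Protocol 2.1 is then needed. If no confirmed infection preceded Visit 3, one sentence saying so closes the point.

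Cost: SAP wording and a little extra analysis, with no new visits or samples, since confirmed COVID-19 is already collected with dates. The supportive table has slightly fewer values. Undiagnosed infections remain, because PCR is scheduled only at screening. The third item does not correct for a patient who was positive before infection but would have become negative by Month 6 without it.

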4.2 Rationale for dose/regimen and duration of treatment

Siponimod

Patients in cohort 1 and cohort 2 are treated with siponimod as part of clinical routine with 2 mg or 1 mg siponimod daily depending on CYP2C9 metabolism status. The siponimod SmPC allows vaccination with non-live or attenuated substances both during continued daily intake of siponimod (cohort 1) or a treatment break for the purpose of the vaccination (cohort 2, duration of treatment break will be around 2-3 months)). In case of a booster vaccination, patients in both cohorts may undergo a treatment break according to SmPC. The decision to continue siponimod treatment or to interrupt the treatment is at the discretion of the treating physician together with the patient independent of AMA-VACC and as part of clinical routine.

Vaccination

Several pharmaceutical companies have received or are awaiting approval of modRNA vaccines including but not limited to BNT162 (Biontech/Pfizer) and mRNA-1273 (Moderna). AMA-VACC participants will be vaccinated with any modRNA vaccine according to the respective EU SmPC at the discretion of the treating physician independent of AMA-VACC. If suggested by local regulations and performed as part of clinical routine any type of booster/refresher vaccination (e.g. mRNA, vector, peptide) is allowed in this study.

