6.3.2 Treatment assignment, randomization

No randomization will be performed in this study. The assignment of a participant to a particular cohort will be coordinated by the sponsor depending on the current MS treatment in clinical routine: Cohort 1: continued siponimod treatment without interruption for the purpose of a SARS-CoV-2 vaccination (except for a booster vaccination). Cohort 2: interruption of siponimod treatment for the purpose of a SARS-CoV-2 vaccination. Cohort 3: first-line MS treatment other than siponimod or no current treatment.

7 **Informed consent procedures**

Eligible participants may only be included in the study after providing, IRB/IEC-approved informed consent.

Informed consent must be obtained before conducting any study-specific procedures (e.g. all of the procedures described in the protocol). The process of obtaining informed consent must be documented in the participant source documents.

Novartis will provide to investigators in a separate document a proposed informed consent form that complies with the ICH GCP guidelines and regulatory requirements and is considered appropriate for this study. Any changes to the proposed consent form suggested by the investigator must be agreed by Novartis before submission to the IRB/IEC.

A copy of the approved version of all consent forms must be provided to Novartis after IRB/IEC approval.

8 Visit schedule and assessments

The Assessment Schedule (Table 8-1) lists all of the assessments when they are performed. All data obtained from these assessments must be supported in the participant's source documentation.

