## 2.7 Analysis of secondary efficacy objective(s)

### 2.7.1 Secondary endpoints

The secondary endpoints are analyzed descriptively within each cohort. The efficacy analysis set is used for all analyses of the secondary parameters.

The semiquantitative SARS-CoV-2 serum functional antibody titer (percent inhibition) is summarized by arithmetic mean, standard deviation, minimum, median and maximum by visit. A boxplot graph will be presented.

The SARS-CoV-2 serum functional antibody titer is summarized by geometric mean, geometric coefficient of variation (CV) and 95% confidence intervals for the (geometric) mean. The Visits Screening, Visit 1/Week 1, Visit 2 /Month 1 and Visit3 /Month 6 are displayed separately in this summary table and a boxplot graph with logarithmic y-axis (log base 10).

The same summary table and boxplot will be provided for the following secondary parameters:

- a) Qualitative and quantitative result of IFNg towards SARS-CoV-2 and towards coronaviridae
- b) Qualitative and quantitative result of IL-2 towards SARS-CoV-2 and towards coronaviridae
- c) Combined response in qualitative INFg or IL-s towards SARS-CoV-2 and towards coronaviridae, i. e. reactive to INFg or IL-2 or to both.
- d) Cell viability, CD3 lymphocytes, CD4 and CD8 cells, percentage of CD4+ and CD8+ cell in peripheral blood mononuclear cells

The percent inhibition values for INFg at screening will be displayed for the subset of patients who are reactive at Week 1 versus non-reactive. The same analysis is provided for IL-2.

All other laboratory data (e. g. number of basal/background spots, spots, quality, comments, mutations) are listed only.

The MS activity is measured by relapses. The crude annual relapse rate until end of study and underlying sums (of relapses and patient-years) will be presented.

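### After a booster, original cohort need not match siponimod status, and the planned Month-6 results are not split by that status

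*Protocol*

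**What the plan says.** **Cohort.** Assignment is made at screening from the MS treatment in clinical routine and the approach to the initial vaccination cycle (Protocol 6.1.3 and 6.3.2). Section 6.3.2 exempts the booster from the no-interruption condition of cohort 1.

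**Booster.** Protocol Section 3 (Vaccination period) states that "siponimod patients in Cohort 1 and Cohort 2 may introduce a treatment break for the purpose of the booster vaccination", and adds a possible reason: "e.g. in case there was no measurable immune response during the initial vaccination cycle". It continues: "The decision for such a treatment break is at the discretion of the treating physician and patient". Section 4.2 repeats the permission: "In case of a booster vaccination, patients in both cohorts may undergo a treatment break according to SmPC".

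**Endpoint.** Table 2-1 sets antibody and T-cell levels at the usual visits and "additionally one month after an optional booster vaccination in participants treated concomitantly with siponimod versus siponimod treatment break versus first-line DMTs".

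**Analysis.** SAP 2.7.1: "The secondary endpoints are analyzed descriptively within each cohort". Its summary table covers Screening and Visits 1, 2 and 3. The SAP's own endpoint list (1.2) leaves out the post-booster time point, although the SAP says it is based on Amendment 2. SAP 2.5.4 notes that several patients were boosted before Visit 3. It adds that seroconversion and IFN-gamma/IL-2 reactivity "were presented for both subgroup of patient who received / did not receive a booster vaccination before Visit 3". SAP 2.2.1 says that no subgroups are examined.

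**The concern.** Cohort answers one question: was siponimod continued or paused around the two initial doses? Under Amendment 2 a cohort 1 patient may pause for the booster. A cohort 2 patient may pause again or, because the break is optional, may not. From the booster onwards cohort is no longer a measure of exposure, but the endpoint is still worded by exposure and the tables are still laid out by cohort.

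The study is meant to inform vaccination of siponimod patients. A boosted cohort 1 row that contains patients boosted during a break could be taken as the response to a booster given on continued siponimod. The reverse could happen in cohort 2. A reader of the planned tables could not tell how far either row is mixed.

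The choice to pause may also depend on the earlier result. The Protocol names a missing response as one example of a reason, and Section 4.5 expects patients to learn their antibody and T-cell results and to use them in booster decisions.

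**Working it through.** The plan gives no figure on this point. Its precision figures (Protocol 12.6.1, SAP Section 3) concern a proportion in 20 patients per arm and do not bear on it. The check is therefore a comparison of the texts, followed by an illustration on assumed rates.

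**1. Where exposure is set and where it is reported**

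| Time point | Siponimod status set by | Planned grouping |
|---|---|---|
| Visit 1 (week 1, primary) | Cohort | Cohort (SAP 2.5.2) |
| Visit 3, not boosted | Cohort for the initial cycle | Cohort; boosted yes/no split |
| Visit 3, boosted before it | Individual decision at the booster | Cohort; boosted yes/no split |
| Booster visit | Individual decision at the booster | None named in the SAP; Table 2-1 wording only |

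The third row is a planned output and does not rely on inference. The booster visit is due one month (+/- 1 week) after the booster and is dropped if it falls within one week of Visit 3 (Protocol Section 8; footnotes to Figure 3-1 and Table 8-1). For patients boosted about a month before Visit 3, that visit is the booster readout.

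**2. Effect on one row**

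Let q be the share of boosted cohort 1 patients who paused, r_p the response rate among those who paused and r_c the rate among those who continued.

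Cohort 1 row = (1 - q) x r_c + q x r_p, so its error as an estimate of r_c is q x (r_p - r_c).

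All rates and shares are assumptions:

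| r_p - r_c | q = 0.2 | q = 0.5 | q = 0.8 |
|---|---|---|---|
| +20 points (80% v 60%) | 4 | 10 | 16 |
| +30 points (80% v 50%) | 6 | 15 | 24 |
| +40 points (80% v 40%) | 8 | 20 | 32 |
| -40 points (40% v 80%) | -8 | -20 | -32 |

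At q = 0 the error is 0 whatever the rates. The last line is there because the sign is not known. If those who pause are earlier non-responders, they need not respond better than those who continue.

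**3. Effect on the contrast between cohorts**

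Let m1 be the share of boosted cohort 1 who paused, m2 the share of boosted cohort 2 who continued, and D the true difference (paused minus continued). If switching is unrelated to outcome:

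Cohort 2 minus cohort 1 = (1 - m1 - m2) x D.

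| m1, m2 | Factor | D = 30 points | D = 20 points |
|---|---|---|---|
| 0, 0 | 1.00 | 30 | 20 |
| 0.10, 0.10 | 0.80 | 24 | 16 |
| 0.25, 0.25 | 0.50 | 15 | 10 |
| 0.50, 0.50 | 0.00 | 0 | 0 |
| 0.75, 0.50 | -0.25 | -7.5 | -5 |

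The contrast shrinks, vanishes when m1 + m2 = 1 and reverses beyond that. If switching depends on earlier response, this formula no longer holds and the direction cannot be predicted.

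**The case against.** The best counter-text is Protocol 12.1. It says participants are analysed by the treatment they received, and then lists an efficacy set after a booster among the sets covered. Table 2-1 is worded by exposure, not by cohort number. Read together, these would allow classification by actual status at the booster. In addition, the cohort 1 definition openly exempts the booster, SAP 2.4.1 counts cohort 1 interruptions up to Visit 3, and no formal comparison between cohorts is planned.

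Part of this stands. The texts allow the right grouping, the results are descriptive, and a careful reader would see that some cohort 1 patients had interrupted. But no rule says how treatment received applies at the booster, and SAP 2.2 repeats the general sentence without the booster set. The interruption counts are separate from the response tables. For cohort 2 there is a single interruption duration around vaccination, with nothing specific to the booster.

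Three stronger readings are tempting, and the documents do not support them:

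- A reader might infer that booster-visit results will be grouped by original cohort. The SAP plans no booster-visit summary, so the first gap there is a missing analysis. Cohort grouping is only inferred from the Protocol wording.
- A reader might infer that those who pause are mainly earlier non-responders. The Protocol offers this as an example only, leaves the choice to physician and patient, and gives no frequencies. That some cohort 2 patients continue siponimod is likewise implied by the optional wording and is not stated.
- A reader might infer that Amendment 2 was written to compare boosters on and off siponimod. It ends recruitment, permits a break and adds a visit to assess the booster response. It poses no such comparison.

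**Conclusion.** The point holds for boosted Month-6 results. Followed as written, the plan can put paused and continued patients in the same row, with nothing in the response tables to separate them. For the booster visit, the plan is silent on both the summary and the grouping.

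The size is unknown. It is nil if every boosted patient kept the siponimod status of the original cohort. Otherwise it depends on the number who changed and on rates the documents do not give. On the assumed rates above, the error in the cohort 1 row runs from 4 to 32 points in absolute value, and either sign is possible. These figures illustrate the mechanism and do not estimate the bias in this trial.

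The week-1 primary endpoint precedes any booster readout and is unaffected. This is a labelling and interpretation fault in descriptive secondary results. It should be corrected, but it does not undermine the main result.

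**What to change.** 1. Define in the SAP a variable for siponimod status at the booster (continued, paused or not determinable), with its derivation from recorded dates and MS-medication status. Table 8-1 already records that status at the booster contact and the booster visit.
2. For siponimod patients, present boosted Visit 3 results, and any booster-visit results, by this status alongside original cohort. Give the number whose status differs from their cohort. Show last pre-booster serostatus descriptively, so that any selection is visible.
3. Say whether the booster visit will be summarised, since Table 2-1 makes it a secondary endpoint and SAP 1.2 and 2.7.1 omit it.
4. State that cohort 1 versus cohort 2 after a booster is not a comparison of continued versus paused siponimod. State also that the status grouping is non-randomised and may depend on earlier response.
5. Reconcile SAP 2.2.1 with 2.5.4, and correct the closing reference in 2.5.4, which puts Visit 3 at Month 3.

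The cost is one derived variable, one added descriptive table and SAP wording. The last SAP revision followed final data review, so the table should be labelled post hoc. The main downside is small cells: status by cohort by serostatus gives 2 x 2 x 2 = 8. Exact 95% intervals have half-widths of about 31 points at 5 of 10, 40 at 2 of 5 and 45 at 1 of 3. Counts should therefore lead, with original cohort kept in view rather than replaced.
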